1.2 Outcomes

The main outcomes regarding the Clinical Study Dossier and clinical study procedures are summarised below.

Inclusion and exclusion criteria

The definition of inclusion and exclusion criteria is based on an extensive literature review and the internal Al-Mind partners` agreement to adhere to the project's objectives.

Definition of MCI at enrolment

General consensus of the criteria to define MCI for the clinical study participants. The inclusion criteria define the degree of cognitive impairment and a minimum of test assessments (table 2).

Ethical requirements and Informed Consent before enrolment

All clinical sites followed the local ethical procedures in alignment with relevant national and EU laws and regulations. An independent Al-Mind ethics advisor has been appointed. Feedback from the user representing association Alzheimer Europe has been implemented.

Ethical Committee approvals

The study has been approved by the Ethical Committees of all clinical sites in due course. The final consensus of the used clinical guidelines, procedures and formation have been incorporated into the application. All Informed Consents have been approved.

Definition of demographic and clinical data collection

Various clinical variables (e.g. demographics, weight, etc.), information about well documented associated pathologies and interventions will be collected. These data will be analysed in order to determine their influence on the risk of progression to dementia for population with MCI.

Blood sample collection, storage and shipment

Blood samples will be collected at the first visit, to determine their APOE allele constellation and individual P-Tau associated P181 and/or P217 protein levels. The samples will be collected, stored and shipped according to standardised procedures (Deliverable 2.1).

Harmonisation of EEG recording and storage

All technological aspects for the EEG recording have been standardised and agreed on among the experts from the five clinical sites. All sites will use identical 128-channel EEG devices and harmonised recording parameters (amplification, sampling rate, filters, artefact recognition, duration of each session etc). The characteristics of the recording environment (baseline noise/light brightness) have been standardised (Deliverable 2.1).

Digitalised Cognitive Testing (CANTAB)

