SOM. Height Please Weigh	ATIC AND NEUROLOGICAL PHYSICAL ASSESSMENT * round up or down to nearest whole cm.
SOM. Height Please Weigh	ATIC AND NEUROLOGICAL PHYSICAL ASSESSMENT t * round up or down to nearest whole cm. t *
SOM. Height Please Weigh Please	ATIC AND NEUROLOGICAL PHYSICAL ASSESSMENT t * round up or down to nearest whole cm. t *
SOM. Height Please Weigh Please Abdon	ATIC AND NEUROLOGICAL PHYSICAL ASSESSMENT t * round up or down to nearest whole cm. t * round up or down to nearest whole kg.
SOM. Height Please Weigh Please Abdon	ATIC AND NEUROLOGICAL PHYSICAL ASSESSMENT t * round up or down to nearest whole cm. t * round up or down to nearest whole kg.
SOM. Height Please Weigh Please Abdon Please	ATIC AND NEUROLOGICAL PHYSICAL ASSESSMENT t * round up or down to nearest whole cm. t * round up or down to nearest whole kg.
SOM. Height Please Weigh Please Abdon Please	ATIC AND NEUROLOGICAL PHYSICAL ASSESSMENT t * round up or down to nearest whole cm. t * round up or down to nearest whole kg.
SOM. Height Please Weigh Please Abdon Please Blood	ATIC AND NEUROLOGICAL PHYSICAL ASSESSMENT t * round up or down to nearest whole cm. t * round up or down to nearest whole kg. ninal circumference * round up or down to nearest whole cm. pressure (systolic)

Blood pressure (diastolic) In mmHg .
Total cholesterol
f available, please provide a recent value (max. 1 year).
Neurological signs *
Other than cognitive symptoms.
O No
O Yes
Please specify the neurological signs
This element is only shown when the option "Yes" is selected in the question "Neurological signs"
Use keywords.
Sleep disorders
O No
O Yes
O Don't know
Burnout or severe stress over time
s it highly probable that the person's cognitive symptoms are caused by burnout or severe stress over time?
O No
O Yes
O Don't know
Page break

Page 9

Mandatory fields are marked with a star *

RISK FACTORS
Dementia
Total number of first-degree relatives with dementia
Include all first-degree relatives with a known dementia condition, both deceased and alive.
Relatives with dementia?
O No
O Yes
O Don't know
Specify the relative who has/had dementia
This element is only shown when the option "Yes" is selected in the question "Relatives with dementia?"
Multiple answers may be selected.
☐ Mother
☐ Father
☐ Sister(s)
☐ Brother(s)
How many sisters are/were affected by dementia?
This element is only shown when the option "Sister(s)" is selected in the question "Specify the relative who has/had dementia"

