Please report the total number of sisters
This element is only shown when the option "Sister(s)" is selected in the question "Specify the relative who has/had dementia"
This number should include both healthy and those affected by dementia

How	many	brothers	are/were	affected	by	dementia?

This element is only shown when the option "Brother(s)" is selected in the question "Specify the relative who has/had dementia"	
Please report the total number of brothers	
This element is only shown when the option "Brother(s)" is selected in the question "Specify the relative who has/had dementia"	
This number should include both healthy and those affected by dementia	
Extrapyramidal pathology	
Relatives with extrapyramidal pathology?	
O No	
O Yes	
O Don't know	
Which relative has/had extrapyramidal pathology?	
This element is only shown when the option "Yes" is selected in the question "Relatives with extrapyramidal pathology?"	
Multiple answers may be selected.	
☐ Mother	
☐ Father	
☐ Sister(s)	
☐ Brother(s)	
How many sisters are/were affected by extrapyramidal pathology?	
This element is only shown when the option "Sister(s)" is selected in the question "Which relative has/had extrapyramidal pathology?"	

Please report the total number of sisters

This element is only shown when the option "Sister(s)" is selected in the question "Which relative has/had extrapyramidal pathology?"
This number should include both healthy and those affected by extrapyramidal pathology
How many brothers are/were affected by extrapyramidal pathology?
This element is only shown when the option "Brother(s)" is selected in the question "Which relative has/had extrapyramidal pathology?"
Please report the total number of brothers
This element is only shown when the option "Brother(s)" is selected in the question "Which relative has/had extrapyramidal pathology?"
This number should include both healthy and those affected by extrapyramidal pathology
Other
Relatives with psychiatric conditions?
Include severe conditions, such as major depressive disorder, schizophrenia, bipolar disorder, etc.
O No
O Yes
O Don't know
Smoking/tobacco use?
O No, never
O Not currently, but previously
O Yes, currently

Age when started smoking?

This element is only shown when the option "Not currently, but previously" or "Yes, currently" is selected in the question "Smoking/tobacco use?" Please round up or down to nearest whole year.				
Age when quit smoking?				

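### The visible inclusion form asks for the number of sisters or brothers only after one is marked as affected, so sibling history cannot be adjusted for sibship size

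*Protocol*

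**What the plan says.** All form items below are in the Protocol, Annex I, inclusion form, Risk factors page.

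- The dementia block opens with an item that has no display condition: "Total number of first-degree relatives with dementia". Its help text reads "Include all first-degree relatives with a known dementia condition, both deceased and alive". No total number of relatives is asked beside it.
- A yes/no/don't-know item on relatives with dementia follows. The checkboxes for mother, father, sisters and brothers depend on it: "This element is only shown when the option 'Yes' is selected in the question 'Relatives with dementia".
- The form then asks "Please report the total number of sisters", under the condition "This element is only shown when the option 'Sister(s)' is selected in the question" on which relative is affected by dementia. The brothers total has the matching condition.
- The help text for these totals is "This number should include both healthy and those affected by dementia".
- The extrapyramidal block is built in the same way.

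On use, Section 1.2 (Outcomes) says that the clinical variables collected will be analysed to "determine their influence on the risk of progression to dementia".

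**The concern.** A total that counts healthy siblings has one evident use, which is as the denominator for the number affected. The display rule collects it only when the number affected is already at least one. Among participants with no affected sibling, an only child cannot be told apart from someone with several healthy siblings, although the second carries much more information about low familial risk.

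The gap also reaches participants with a positive history. Someone with an affected sister and only healthy brothers supplies a sister total but no brother total, so the sibship is incomplete.

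At stake is a candidate risk factor for progression. If sibling history is used as a yes/no or a count, it partly measures how many siblings there were to become affected. The size needed to adjust for this is missing according to the answer itself. The totals that are recorded come almost entirely from sibships with an affected member, so they are a poor basis for imputing the others.

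**Working it through.** The protocol gives no figure on this point, so there is none to reproduce. The check traces the form logic and then illustrates the consequence.

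**1. Form logic (dementia block, same parental answers)**

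| Participant | Sister total | Brother total |
|---|---|---|
| No siblings | not shown | not shown |
| Several healthy siblings | not shown | not shown |
| Affected sister, only healthy brothers | recorded | not shown |
| Affected sister and affected brother | recorded | recorded |

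The first two rows are identical. The one visible exception is a participant without a demented sibling who has a sibling with extrapyramidal pathology. That person supplies a total through the other block.

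**2. Dependence of sibling history on sibship size**

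Assumption, not in the documents: each sibling has the same independent probability p of known dementia. The chance of at least one affected among k siblings is 1 − (1 − p)^k.

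| p | k = 1 | k = 4 | k = 6 | Ratio, 6 to 1 |
|---|---|---|---|---|
| 0.05 | 0.050 | 1 − 0.95^4 = 0.185 | 1 − 0.95^6 = 0.265 | 5.3 |
| 0.10 | 0.100 | 1 − 0.90^4 = 0.344 | 1 − 0.90^6 = 0.469 | 4.7 |

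Familial risk per sibling is the same along each row. Only the number of siblings changes.

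**3. Any affected parent or sibling**

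Further assumption: each parent is affected with probability q. The chance is 1 − (1 − q)^2 (1 − p)^k.

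| q | p | k = 1 | k = 6 | Ratio |
|---|---|---|---|---|
| 0.30 | 0.05 | 1 − 0.49 × 0.95 = 0.53 | 1 − 0.49 × 0.735 = 0.64 | 1.2 |
| 0.30 | 0.10 | 1 − 0.49 × 0.90 = 0.56 | 1 − 0.49 × 0.531 = 0.74 | 1.3 |
| 0.10 | 0.05 | 1 − 0.81 × 0.95 = 0.23 | 1 − 0.81 × 0.735 = 0.40 | 1.8 |
| 0.10 | 0.10 | 1 − 0.81 × 0.90 = 0.27 | 1 − 0.81 × 0.531 = 0.57 | 2.1 |

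The two parents are a fixed denominator, so they dilute the dependence on family size.

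**4. How often the sister total would be recorded in the dementia block**

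Assumption: the number of sisters is Poisson with mean m between 0.75 and 1.5. The share of participants shown the field is 1 − exp(−mp).

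- At m = 1 and p = 0.10: 1 − exp(−0.10) = 0.095, about 95 of the planned 1000 participants.
- Over p = 0.02 to 0.20 and the range of m: from 1 − exp(−0.015) = 0.015 to 1 − exp(−0.30) = 0.259, about 15 to 259 of 1000.

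Among those not shown the field, the share with no sister at all is exp(−m(1 − p)). This runs from exp(−1.47) = 0.23 (m = 1.5, p = 0.02) to exp(−0.60) = 0.55 (m = 0.75, p = 0.20). The hidden group is therefore a real mixture of participants with no sister and participants with healthy sisters only.

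**The case against.** The display conditions are not in dispute. The case against concerns how much follows from them, and most of it stands.

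- **Size.** A reader might take the roughly five-fold spread as applying to family history as a whole. It applies only to sibling history, for one sibling against six. The form's headline items cover all first-degree relatives, and once parents are included the spread is much smaller (step 3).
- **Confounding.** A reader might infer that family history is confounded with family size. The documents do not show that. Bias in the association with progression requires family size itself to be related to progression; otherwise the effect is misclassification or dilution. Nor do the documents say that family size differs between the participating countries.
- **Beyond repair.** A reader might conclude that family history is unusable. It is not, because mother and father have their own checkboxes and parental history can be analysed free of sibship size.
- **Importance.** The protocol nowhere says that an affected fraction will be formed. Section 1.2 does not name family history among its examples, and neither does the list of possible confounders in Section 3.2. It is not a named Predictor input, and these dementia items are not marked as mandatory.
- **Unseen pages.** The readable form breaks off in the comorbidity section, and the sociodemographic items scheduled in Table 3 are not shown. An unconditional sibling count elsewhere cannot be excluded. That the form asks for the total conditionally in two separate blocks makes one less likely.

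What survives is that, in the visible form, the display rule defeats the purpose of a field that the form already contains.

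**Conclusion.** The point holds as a minor flaw in the form's branching, limited to the sibling part of family history. In what can be read, sibling totals are collected almost only from participants with an affected sibling, so sibling history varies with sibship size and cannot be adjusted for it.

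The size in steps 2 and 3 rests on assumed per-sibling and per-parent risks, with independence between relatives. The documents supply none of these. The form logic itself needs no assumption beyond there being no unconditional sibling count on a page not shown. Parental history and the primary endpoints are untouched.

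**What to change.** Ask for total sisters and total brothers once, of every participant, with zero allowed, outside both conditional blocks. First check that no page of the form already does so. Repeating the question inside each block is unnecessary, because the sibship is the same for both conditions.

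For participants already enrolled, collect the two numbers at the next scheduled visit. Table 3 lists risk factors at both screening and T0, so those not yet at T0 can be asked there. Analyse sibling history as number affected out of total, separately from parental history.

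The cost is two extra numeric fields, an update of the national electronic forms described in Section 3.6, and a brief back-collection.
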